1.0 Study Summary

1.1 Please provide a brief summary of the study in the table below. A complete description of the study with detailed information should be provided in the body of the protocol. For sections not applicable to the study, mark them as N/A.

Study Title	Brasthesis Prototype for Women Veterans with Upper Limb	
-	Amputations	
Study Design	Prospective, Case series	
Primary	To evaluate the satisfaction of and function and comfort with	
Objective/Purpose	Brasthesis.	
Secondary	To compare Brasthesis to the amputee's traditional harness.	
Objective(s)/Purpose		
Research	Use of a sports bra as a gender-specific harness for upper	
Intervention(s)/	limb prostheses	
Investigational		
Agent(s)		
IND/IDE #	N/A	
ClinicalTrials.gov	Pending	
NCT#		
Study Population	Women with a unilateral upper limb amputation	
Sample Size	10	
Study Duration for	8 weeks (4 weeks for fitting and 4 week wearing period)	
individual subjects		
Study Specific	CPRS - Computerized Patient Record System	
Abbreviations/	FY – Fiscal Year	
Definitions	HIPAA – Health Insurance Portability and Accountability	
	Act	
	IRB – Institutional Review Board	
	JAHVH – James A. Haley Veterans' Hospital	
	PHI – Protected Health Information	
	PI – Principal Investigator	
	PM – Project Manager	

Page 3 of 18

Revised: July 6, 2023

2.0 Objectives

- 2.1 a. Evaluate the satisfaction of and function and comfort with Brasthesis.
 - b. Use goniometry measures of range of motion and pressure mapping to compare range of motion and interface pressure of Brasthesis with the traditional harness.
- 2.2 No hypotheses will be tested in this pilot proof-of-concept study.

3.0 Background

3.1 Female Anatomy and Prosthetic Harness.

Limitations exist with the current traditional chest strap due to female anatomy. We know from the sports [1] and seat belt/airbag [2] literature that breast tissue injuries can disrupt the blood flow to the breast resulting in swelling, significant blood loss, hematoma, fat necrosis, and oil cyst hematoma. Injury to the mammary ducts can affect the future or current flow of breast milk [3]. More commonly, smaller superficial arteries along with veins become injured, leading to more localized injury and less serious bleeding and bruising. While there is no known research on whether a prosthetic harness can cause injury to breast tissue, we know that frequent wearing of tight clothing [4] can cause bruising, swelling, and thrombophlebitis. Further, regular physical activity is important in maintaining fitness, injury prevention, and overall well-being. Even without the additional pressure of a prosthetic harness, 50% of women report suffering exercise-induced breast discomfort during exercise which leads to reduced physical activity participation [1].

Both males and females with upper limb loss [5] report musculoskeletal pain, with no difference in reported pain between prosthetic wearers and non-wearers. Women with large breast sizes also report an increased prevalence and severity of musculoskeletal pain exacerbating the pain already caused by amputation(s), a problem exacerbated over the past decade as the mean bra size has increase from a 12B to a 14C; 25% of bras sold are now a D cup or larger [6]. Age is an additional risk factor. Beginning about age 45, breast skin thickness decreases significantly [7]. Breast skin elasticity begins to decrease in the mid-twenties [7]. Gender Comparisons.

Satisfaction in Women with Limb loss (Non-Veteran). Most of the prosthetic satisfaction literature includes men and lower limb loss. In a sample of 362 participants with upper and lower limb trauma-related above elbow amputations (78% men) [8], 30% were dissatisfied with the comfort of their prosthesis. Women were less likely to be satisfied with fit, comfort and appearance [8]. Similarly, of 181 upper limb prosthesis wearers (86% men) [9], nearly 20% were dissatisfied with their prosthesis. Most used their prosthesis for about half of the tasks performed in everyday life [9].

Rejection. In a study [9, 10] of 199 non-Veterans with upper limb loss (84% men), 25% of women and 11% of men discontinued wearing their upper limb prosthesis. The main reasons were dissatisfaction with comfort, function, and control. Discontinued use was more likely in more proximal amputations and in women [10]. In a second study [11] of 191 non-Veterans with upper limb loss (51% men), 31%, not stratified by gender, discontinued wearing their prosthesis. In both studies [9-11], 29% of the sample had an elbow or more proximal amputation. There are no known publications with women as the sole sample, although it is believed that this research is in progress.

A study [12] of 776 Veterans with upper limb loss (97% men) found that women were less likely to have ever used a prosthesis or received training in use of the prosthesis, more likely to use a cosmetic prosthesis, and less likely to use a body-powered prosthesis when compared to men. Device heaviness or fatigue was the most common reason for discontinued use. There were however only two women Veterans with forequarter or shoulder disarticulation enrolled in the study. Another study [13] of 196 Veterans with upper limb loss (98% men) found 40% with transhumeral amputations and 50% with shoulder disarticulations did not use a prosthesis. Prosthetic use was most frequently discontinued because of discomfort, pain, and weight of the device.

A study [14] of 242 males and females with upper limb loss that included 68 (28%) individuals with humeral amputation/shoulder disarticulation found that 80% of women with high-level amputations and 15% of men with high-level amputations discontinued use of their prosthesis. Ninety-five percent of participants reported comfort as a reason for discontinued use. In summary, we only have data for a few women with proximal upper limb amputations and disarticulations. The literature overall identifies comfort as a problem for women with upper limb amputations. Socket Fit.

The term 'socket fit' encompasses the factors that impact prosthetic comfort and stability on the residual limb [15]. Fit and associated comfort have a substantial effect on user satisfaction and prosthetic use [15]. The socket is the crucial junction where the soft tissue of the user's residual limb interfaces with the rigid materials of the prosthesis. Socket fit must, for our purposes, accommodate the female anatomy as well as position the prosthetic device to efficiently transmit intended movements [15]. Socket fit also includes appropriate distribution of pressure across the residual limb. While compression can increase mechanical stability, it can also cause discomfort, tissue irritation, and damage. This challenge is increased for individuals with proximal amputations as the weight of the prosthesis amplifies the demand of the socket and the residual limb [15]. We believe that BrasthesisTM may relieve uncomfortable pressure at the residual limb by increasing the contact area of the harness to include the sports bra. The Revolutionizing Prosthetics 2009 program [16] offered a solution similar to BrasthesisTM to the problem of the tightening around the intact shoulder required by the traditional harness [16]. Recognizing that secure attachment to the body and distribution of weight are critical to comfortable fit and function, designed a shoulder-level socket with full fabric, tee shirtlike suspension.

Socket Pressure.

Accuracy and repeatability of the Tekscan F-Socket has been shown to be accurate with good reliability [17]. Daly et al. [18] were perhaps the first to use the pressure mapping with upper limb amputation research. No correlation was found between patient report of discomfort and pressure data. Schonfield et al. [15] built on the limitations of the Daly study to successfully characterize pressure distribution patterns unique to the participants socket designs. While using pressure mapping to better understand socket-fit is in its early stages, we believe that pressure mapping may be a useful tool to compare harness and socket pressure when wearing BrasthesisTM with the traditional prosthesis. We are not using pressure mapping to measure absolute values, rather, our focus is on how the harness distributes pressure and positions the socket on the residual limb and

thus influencing pressure distribution. [name] will provide expertise on pressure mapping on the proposed project

4.0 Safety Endpoints

4.1 Primary endpoints are satisfaction, function, and comfort.

The secondary endpoints are the interface pressure that drives comfort and range of motion that drive functional movement.

Page 7 of 18 Revised: July 6, 2023

5.0 Study Interventions, Investigational Agents, and FDA-Regulated Products (as applicable)

- 5.1 The study intervention is our patent-pending harness that we have named 'Brasthesis' for women amputees. The patent was submitted 12/6/2021. Brasthesis adapts a heavy-duty sports bra to replace commercially available prosthetic harnesses. See photos of commercially available, top, and Brasthesis below.
- 5.2 Drug/Device Handling: N/A. While a prosthesis is considered a device, the harness attaching the prosthesis to the residual limb is not considered device.

Devices	Drugs/Biologics
☐ FDA Approved Device – Approved Use	☐ FDA Approved Drug/Biologic – Approved Use
☐ FDA Approved Device – Unapproved Use	☐ FDA Approved Drug/Biologic — Unapproved Use
☐ Investigational Device – Non-Significant Risk	☐ Investigational Drug/Biologics
☐ Investigational Device – Significant Risk	□ Placebo
☐ Humanitarian Use Device Exemption	☐ Other Drugs/Biologics
☐ Other Devices	

5.3 N/A.

5.4 N/A.

5.5 N/A.

6.0 Procedures Involved

6.1 This project will use a case series design to fit five women with unilateral upper limb loss with Brasthesis (harness). The proposed project will offer three fitting options: (1) We will fit patients face to face at the James A Haley VA Hospital (JAHVH), (2) We have requested travel funds to bring patients, caregiver (if necessary), and clinical staff to JAHVH for fitting, an option we found successful with previous prosthetic arm studies, and (3) We will use a VA

approved video conferencing system/software, e.g., Veteran Video Connect, with the research team at one location and the patient and patient's prosthetic team at a second location (as we did for our prototype during the COVID-19 restrictions). Option 3 will only be used if we have difficulty recruiting with options 1 and 2.

6.2 Outcomes data will be collected via survey and brief interview. Pressure mapping and range of motion data will be collected using pressure mapping technology and a goniometer. One focus group will be held after all patients have been fitted. All data will be analyzed descriptively. Subjects will be given the option to consent to having photos taken post intervention for educational and/or technology development purposes.

6.2

⊠ Audio/Video Recording	□Physical Exam
□Blinding	□Radiation or Radiation-Producing
	Machines (e.g. X-ray, CT, etc.)
□Control Group	□Radioactive Materials (e.g.
	Radiopharmaceuticals)
□Deception	□Randomization
⊠Focus Groups	⊠Record, Chart, or Dataset Review
⊠Follow-Up Call	□Specimen Analysis
⊠Interviews	□Specimen Collection
□New Innovative Practice/Therapy	⊠Surveys and/or Questionnaires
□New Investigational Procedure (e.g. a new surgical procedure)	□Other Biomedical Procedures

- At baseline, after signing of informed consent, the project manager will work with the participant over the phone to order two bras from the Shefit® website, using sizing provided on the website. One Shefit® bra will be for the participant to wear and the other bra will be deconstructed for strapping and d-rings.
- During this baseline phone meeting, the project manager will ask how many days
 per week and hours per day the participant wears their prosthesis with traditional
 harness. The project manager will explain, as delineated in the informed consent
 document, that she will contact the participant weekly during the four-week wear
 period for the purpose of checking in, i.e., checking on Brasthesis wearing time
 and problems that may have occurred during the week.
- During this baseline phone meeting, the two sub-surveys of the Orthotic and Prosthetic User Survey (OPUS) and the one-item Socket Comfort Scale will be administered. The socket comfort scale is a one-item analog 0-10 self report rating scale. There is no published pdf for this one-item scale. The score is included in the Data Collection Sheet Item #12.
- The project manager will extract demographic and clinical information from the medical record.

- The participant will be scheduled for a fitting at a prosthetic clinic, either at the JAHVH study site or their home VA prosthetic clinic, the clinic regularly attend in/ near their place of residence. The fitting process will begin with introductions. The participant will don the prosthesis/traditional harness. We measure functional range of motion (shoulder flexion/extension and abduction/adduction) with a goniometer while participants are wearing their conventional prosthetic harness.
- Also at the fitting visit, we will use the Tekscan Artec Studio system to quantify pressure between the prosthetic socket and residual limb and around the contralateral axilla while wearing the traditional harness. Pressure mapping entails attaching a paper thin, flexible sensor, trimmed to match anatomical contours with double sided adhesive tape directly to the skin to securely cover each participant's residual limb and in the contralateral axilla region then mapping pressure at three positions: (1) prepressure will be measured wearing the prosthetic liner with the residual limb positioned neutral at their side, (2) wearing prosthesis with 90 degrees prosthetic elbow flexion, and (3) full elbow extension with shoulder flexion in the plane of the scapula [5].
- The subject will then don the Shefit® bra over the traditional harness. We will mark where the traditional harness and Shefit® overlap. D-rings from the spare bra will be riveted at the marked spots (for our prototype, the patient required two d-rings anterior and posterior). Once the d-rings have been riveted to the prosthesis, the participant will don modified Shefit bra/Brasthesis. At this point the custom fitting will begin which will vary from participant to participant. Our prototype patient had gaping at the top of the socket that was successfully addressed by adding a strap from the spare bra cross the participant's back. The participant guided the prosthetist as to where she needed support. The prosthetist riveted a third central d-ring to accommodate a diagonal backstrap. This individualization may vary for each of the five subjects and is the primary purpose for this proof of concept study.
- We will replace the front zipper with a commercially available magnetic bra closure for one-handed donning, if desired
- Participants will be provided a Jawbone UP 24 or OPOS1 activity tracker by the
 prosthetist once the prosthesis has been successfully fit using Brasthesis. Jawbone
 API software or OPOS1 software provides direct export of accelerometer that
 contains no PHI or PII (deidentified) data to approximate wear time to the hour of
 each day.
- The prosthetic and research teams will be available should the participant need adjustment to the harness and prosthetic fit, per standard care.
- At the end of the four-week wearing period, the participant will return to the clinic. Range of motion measurement and pressure mapping will be repeated but this time with the Brasthesis rather than the traditional harness.

- The outcome measures administered at baseline will be completed again post-intervention. The project manager will conduct a brief interview for the participant and prosthetic team to understand the experience of being fit with and using Brasthesis. This interview will be audio recorded.
- The participant will be told that after all five participants have completed Brasthesis, a focus group will be held for the purpose of brainstorming how to proceed with the manufacturing and marketing of Brasthesis. This focus group will be audio recorded.
- 6.3 All procedures will be performed solely for research purposes except for the prosthetic clinic visits for Brasthesis and prosthetic adjustment as needed. Returning to the amputation clinic for Brasthesis/harness or prosthetic adjustment are standard care.
- 6.4 Participants will be under the care of experience amputee and prosthetic clinicians including occupational therapists, physicians, prosthetists, and engineers who will be able to efficiently and empathetically address any challenge that may occur during the Brasthesis fitting process and wearing period.

Participants can return to the use of their traditional harness at any time. They will not be withdrawn from the study if they return to using their traditional harness as data on why participants use or do not use Brasthesis are needed to address research questions.

Participants can contact the project manager, an occupational therapist with extensive upper limb amputation and prosthetic experience, at any time.

- 6.5 Aim one of this project will capture existing data:
 - Data to be collected is displayed in the Table below and the uploaded data capture sheet.

Table 1 Variables			
Variable	RQ	Definition	Source, Timepoint
		Outcomes	
Wearing time	1.1	Days/week, hours/day, Traditional versus Brasthesis™	Weekly communication
		Jawbone Up 24 or OPOS1 activity tracker	Automated
Satisfaction	1.2	OPUS Satisfaction with Device	
Function	1.3	OPUS UE Functional Status [22] (Appendix 5)	Traditional – pre
Comfort	1.4	Socket Comfort Score [23], 0-10 numeric rating scale	Brasthesis - post
Barriers	1.5	Described by participants and clinicians	Post interview (QL)
Pressure	2.1,2.2	Tekscan F-Socket (Appendix 7)	Prosthetist, engineer, post
Demographic and Clinical Variables			
Age		Age on date of baseline data collection	
Sex		Male, female, other	
Race/ethnicity	All	Caucasian, African American, Hispanic,	CPRS, baseline interview
Time since		In years: index event – date at baseline	
Amputation		transhumeral, shoulder, interscalulothoracic	

Prosthesis type	Myoelectric, hybrid, cosmetic		
Bra size	Size of She-fit® bra ordered		
	nd Prosthetics User's Survey, UE=upper extremity, QL=qualitativ red Patient Record System	ve,	

- 6.6 No biological specimens will be collected.
- 6.7 The only semi-long-term follow-up will be the focus group once all five participants have completed the 4-week wearing period. The focus group will be audio recorded using the TEAMS recording feature. Once transcribed, the audio recording will be destroyed.
- 6.8 No Humanitarian Use Devices (HUD).

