9.0 Study Timelines

- 9.1 It should take up to 2-4 weeks to fit Brasthesis (one to three prosthetic clinic visits). The Brasthesis wearing period is 4-weeks. Data collection could add a week before and a week after the wearing period depending on scheduling.
- 9.2 The entire project will take one to two years including dissemination of findings.

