Brasthesis[™] Prototype for Women Veterans with Upper Limb Amputations

NCT ID: NCT05179395

IRB ID: STUDY003630 IRB Approval Date: 02/10/2022

Data Collection and Analysis

Aim 1. After signing of informed consent and during the same phone conversation as configuration of the bra order, the project manager will administer the baseline measures and obtain demographic and clinical data not available in the Computerized Patient Record System (CPRS). See Table 1. *The project manager will ask how many days per week and hours per day the participant wears their prosthesis with traditional harness (Aim 1, Research Question (RQ) 1.1)*. The project manager will explain, as delineated in the informed consent document, that she will contact the participant weekly during the fourweek wear phase for the purpose of tracking *Brasthesis*[™] wearing time. We will also employ an activity tracker as a quantitative proxy of prosthesis wear time. Similar systems have been employed in other prosthesis studies [20, 21] and the software provides direct export of accelerometer data to approximate wear time to the hour of each day. Participants will be provided a activity tracker by the prosthetist once the prosthesis has been successfully fit using Brasthesis[™]. The pre to post change ordinal data will be analyzed using quantitative descriptive analyses.

Other outcomes with valid and reliable measures include: satisfaction, measured with the Orthotic Prosthetic Users Survey (OPUS) Satisfaction with Device Scale [22] (Appendix 4), function, measured with the OPUS Upper Extremity Functional Status Scale [22] (Appendix 5) and comfort, measured with the Socket Comfort Score [23], a numeric rating 0-10 scale where 0 is the least comfortable and 10 the most comfortable). See Appendix 6 for our initial data coding plan. The pre to post change ordinal data will be analyzed using quantitative descriptive analyses. The results will be tabled and graphed.

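### RQ 1.1 compares one recalled answer on traditional-harness wear with four weeks of prompted reports and a tracker that cannot tell which harness is worn

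*Protocol*

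**What the plan says.** Table 1 (Protocol 6.5 and SAP) lists wearing time as an outcome under RQ 1.1, in days and hours, traditional against Brasthesis. The SAP (Aim 1) plans a descriptive pre-to-post analysis.

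- **Traditional harness.** In the baseline call the project manager asks "how many days per week and hours per day the participant wears their prosthesis with traditional harness" (SAP, Aim 1; Protocol 6.2 has the same question). No other collection of traditional wear is described in the text.
- **Brasthesis, self-report.** At that call the participant is told that "she will contact the participant weekly during the four-week wear" "period for the purpose of checking in, i.e., checking on Brasthesis wearing time", and on problems during the week (Protocol 6.2).
- **Brasthesis, tracker.** The device is handed over by the "prosthetist once the prosthesis has been successfully fit using Brasthesis" (Protocol 6.2). The SAP has it taken off the prosthesis when the four weeks end.
- **Switching.** "Participants can return to the use of their traditional harness at any time" (Protocol 6.4), and those who do so stay in the study.
- **Eligibility.** Women who have given up their prosthesis may enrol (Protocol 10.2).

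Neither document says which Brasthesis source is set against the baseline answer, or how tracker hours are assigned to a harness.

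**The concern.** A pre-to-post change describes the harness only if both sides are measured in the same way. Here one side is a single statement of usual use. The other is a series of reports from women who know that they will be asked each week. Regular questions about wear can plausibly raise actual or reported wear, and only the Brasthesis side receives them. The study has no control group that would show such an effect.

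The tracker adds a separate difficulty. It is attached to the prosthesis, so it registers use under either harness. A woman who goes back to her traditional harness would still accumulate tracker hours, and these could be read as Brasthesis wear. That would happen in exactly the women whose experience counts against the new harness. With five participants needed (Protocol 12.2), each woman's change will be read directly from the tables and graphs.

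**Working it through.** The documents give no mean, spread, recall error or tracker accuracy for wear time, and the plan has no figure to reproduce. The check is therefore a count of measurements and an accounting of what the planned change contains.

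**Counts per participant**

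| | Traditional, before Brasthesis | Brasthesis period |
|---|---|---|
| Self-reports of wear | 1 | about 4 (weekly for 4 weeks) |
| Weekly contacts about wear | 0 | about 4 |
| Tracker days | 0 | up to 4 × 7 = 28 |

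**What the self-report change contains.** Let W_T be true usual wear with the traditional harness and W_B true wear with Brasthesis in the absence of calls. Let p be the effect of weekly contact, e0 the error in the single baseline answer and e1 the average error in the weekly reports. The observed change is then

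D = (W_B + p + e1) − (W_T + e0) = (W_B − W_T) + p + (e1 − e0).

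Only the first term belongs to the harness. Prompting makes p plausibly positive. The sign of e1 − e0 is unknown. If traditional wear is also asked about weekly, p appears on both sides and cancels as far as it is equal, and both errors come from the same kind of question.

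**What the tracker contains.** Let B and H be hours worn with Brasthesis and with the traditional harness during the wearing period. The tracker approximates T = B + H. A woman who has reverted fully has B = 0 and T = H, which looks the same as full Brasthesis use with T = B. Only a question asked by harness separates the two.

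**Women who had abandoned the prosthesis.** If W_T = 0 and the baseline answer is 0, D cannot be negative. Any use counts as an increase, whatever its cause.

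**Room for matched calls.** The bras are ordered at the baseline call and the fitting visit follows. The interval between them is not stated. For the fitting itself Protocol 9.1 says "It should take up to 2-4 weeks to fit Brasthesis", over one to three visits, and allows for about a week of data collection before the wearing period. If the interval before the first fitting is 1 to 4 weeks (assumption), matching means 1 to 4 added calls per woman: 5 to 20 calls for five women, or 10 to 40 if all ten are recruited.

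**The case against.** Wear time is peripheral. It is absent from the objectives in section 2.1 and from the endpoints in section 4.1. Section 2.2 rules out hypothesis tests and section 17.1 limits the analysis to description. No error rate, sample size or decision depends on RQ 1.1. All of this stands and limits the weight of the point. It does not make the two sides comparable.

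Self-report exists on both sides, and the SAP summarises tracker data separately. A reader might infer that the plan subtracts the recalled answer from tracker hours; neither document says so. What remains is that the source to be compared is not named, and that a self-report comparison still sets one answer against about four prompted ones.

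Table 1 gives weekly communication as a source for the traditional-against-Brasthesis row, which might mean that wear is asked by harness each week. The procedures describe only the baseline question for the traditional harness and weekly questions about Brasthesis. If more is intended, the text should say so.

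A reader might also infer that the tracker should simply be issued at consent. That is not practical as a general rule. Consent is mostly by phone and mail (Protocol 22.2), the prosthetist supplies the tracker, fitting may take a single visit, and fitting modifies the prosthesis. Finally, calls before fitting may themselves change usual wear, above all in women who had stopped using the prosthesis. This is a fair reason to keep the first, unprompted answer on file beside the weekly ones.

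**Conclusion.** The asymmetry is in both documents and nothing elsewhere offsets it: 1 self-report and 0 tracker days against about 4 self-reports and up to 28 tracker days per woman. A rise in wear time could partly reflect prompting or recall, and tracker hours can include traditional-harness use.

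A reader might go further and conclude that the comparison is shown to be biased in favour of Brasthesis by some number of hours. The documents do not support that. They contain nothing from which a size could be derived, and the direction of the recall component is unknown. That prompting raises wear is a plausible assumption, not a finding. The point concerns the interpretation of a listed descriptive outcome and leaves the section 4.1 endpoints and the sample size unaffected.

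**What to change.** This is a cheap improvement to the protocol and SAP.

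1. Between consent and the first fitting visit, make the same weekly call with the same days-and-hours question about the traditional harness. Use these answers as the baseline for RQ 1.1.
2. In every wear-period call, ask days and hours separately for Brasthesis and for the traditional harness. Use the answers to indicate how much of the tracker total belongs to each.
3. State in the SAP that the traditional-against-Brasthesis comparison is weekly self-report against weekly self-report. Report tracker data only as total prosthesis wear in the Brasthesis period.
4. Show women who had abandoned their prosthesis separately, since their baseline may be zero.
5. Earlier tracker issue is optional, and only where a clinic visit precedes modification of the prosthesis.

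The cost is a few short calls by the project manager per participant and an update to the contact schedule described in the consent document. The existing calls, including their check for problems, stay as they are. Matching reduces one-sided prompting but cannot remove it entirely, because the two periods still follow one another without a control group; the report should say so.

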OPUS=Orthotics and Prosthetics User's Survey, UE=upper extremity, QL=qualitative, CPRS=Computerized Patient Record System					

Aim 2. An effective harness must help hold the prosthetic socket securely on the limb, facilitate a functional range of motion, and remain comfortable when worn [26]. Therefore, on the day of the post wearing period group interview, we will perform a series of quantitative tests to characterize how Brasthesis [™] affects key biomechanical measures related to prosthesis fit, function, and comfort. We will first quantify the functional range of motion participants can achieve while wearing Brasthesis [™] and their conventional prosthetic harness. Movements relevant to upper limb prosthesis use such as maximum shoulder flexion/extension and abduction/adduction values [27] will be captured using goniometers and these values compared across both harnessing systems. As Brasthesis [™] is designed to accommodate female anatomy, we anticipate it will not encumber range of motion when compared to a conventional harness and likely even improve it.

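### If the prosthesis is adjusted between the two comfort ratings, the Socket Comfort Score change mixes that adjustment with the harness effect

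*Protocol*

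**What the plan says.** **Design and aims.** Protocol 1.1 describes the study as "Prospective, Case series" and gives its secondary objective as "To compare Brasthesis to the amputee's traditional harness". Section 4.1 makes satisfaction, function and comfort primary. Section 2.2 rules out hypothesis tests, and 12.2 says five women are needed.

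**Timing of the comfort rating.** Under Protocol 6.2, on the baseline phone call and before any clinic visit, "the one-item Socket Comfort Scale will be administered". After the wearing period, "The outcome measures administered at baseline will be completed again post-intervention". Table 1 (Protocol 6.5, repeated in the SAP) lists the measure as "Socket Comfort Score [23], 0-10 numeric rating scale", with the pre rating for the traditional harness and the post rating for Brasthesis.

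**What may happen in between.** Protocol 9.1 allows one to three fitting visits over two to four weeks, then four weeks of wear. Section 6.2 states: "The prosthetic and research teams will be available should the participant need adjustment to the harness and prosthetic fit, per standard care". Section 6.3 likewise treats return visits for harness or prosthetic adjustment, where needed, as standard care.

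**Analysis.** SAP Aim 1 describes the pre-to-post change in the ordinal scores, tabled and graphed. Table 1 has no adjustment variable and no later rating of the traditional harness.

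**Same-day testing.** SAP Aim 2 measures range of motion under both harnesses on the day of the post-wear interview, with "these values compared across both harnessing systems", and compares pressure maps in the same way. Protocol 6.2 differs: it measures the traditional harness at the fitting visit and repeats the measurements at the end with Brasthesis only.

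**The concern.** The two ratings differ in more than the harness. The pre score describes the traditional harness on the prosthesis as it was at the baseline call. The post score describes Brasthesis on the prosthesis as it stands some weeks later, possibly after adjustment. The item asks about socket comfort, and Protocol 3.0 itself ties socket fit to comfort, so a change in prosthetic fit could move the score whichever harness is worn. The traditional harness is never rated again once any adjustment has been made.

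At stake is how a primary endpoint is read. A better comfort score would naturally be credited to Brasthesis, although part of it could come from adjustment available under either harness. With five women, one such case is visible in the table and graph.

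**Working it through.** The documents give no comfort effect, standard deviation or adjustment frequency, so there is no plan figure to reproduce. The check is what the planned ratings can identify, followed by an illustration of size.

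**1. Interval between ratings.** From Protocol 9.1: 2 + 4 = 6 weeks to 4 + 4 = 8 weeks, before any scheduling slack.

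**2. What the planned change contains.** For one woman, write H for the harness effect (including the customisation that belongs to Brasthesis), A for the effect of any other prosthesis adjustment, and T for time and everything else.

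- Planned: Brasthesis post − traditional pre = H + A + T.

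That is one difference for up to three unknowns. If her prosthesis is not adjusted, A = 0 and this concern does not arise for her.

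**3. Whether other planned data separate H from A.**

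- Range of motion and pressure under both harnesses (SAP Aim 2): not comfort ratings.
- Weekly calls about problems (Protocol 6.2), and the post interview on fitting barriers and comparison with the traditional prosthesis (SAP Aim 1): may identify adjusted women, but give no point value for A.
- Data collection sheet and SAP Appendix 6: not in the text available, so an adjustment field there cannot be excluded. Such a field would identify women, not measure A.

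**4. Size, under assumptions.** If k of 5 women each gain a points from adjustment alone, the mean change shifts by k × a / 5. Both k and a are assumed; the documents give neither.

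| Women adjusted (k) | a = 1 point | a = 2 points |
|---|---|---|
| 0 | 0 × 1 / 5 = 0 | 0 × 2 / 5 = 0 |
| 2 | 2 × 1 / 5 = 0.4 | 2 × 2 / 5 = 0.8 |
| 5 | 5 × 1 / 5 = 1.0 | 5 × 2 / 5 = 2.0 |

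The mean serves only as an illustration, since the SAP calls these data ordinal and names no summary statistic. A median change would shift by between 0 and a.

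**5. What one more rating adds.** Suppose the traditional harness is also rated at the post visit, on the same prosthesis. Let S be whatever is peculiar to that rating: brief wear, order, recall, and a prosthesis customised for Brasthesis. Then:

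- Traditional post = traditional pre + A + T + S.
- Brasthesis post − traditional post = (H + A + T) − (A + T + S) = H − S.
- Traditional post − traditional pre = A + T + S.

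The paired difference is free of A and T. S remains, so the two contrasts should be shown together.

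**The case against.** The strongest reply is that this is a descriptive proof-of-concept study without hypothesis tests. Co-intervention is inherent in any uncontrolled before-and-after series, and Protocol 2.1b names range of motion and pressure, not comfort, as the measures to compare between harnesses. That stands as a limit on the consequence: no error rate or power is affected. But comfort is still primary, and its pre-to-post change is the planned quantitative result.

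A second reply is that customisation is the intervention. Protocol 6.2 calls individualised fitting the main purpose of the study, and its one worked example, gaping at the top of the socket, was solved with a strap. This also stands. D-rings, straps and any fit change needed to make Brasthesis work belong to H. An adjustment correcting a problem that Brasthesis caused would not be an unrelated gain either. The concern covers only other changes to the prosthesis.

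A reader might go further and infer that fitting visits routinely rework the socket, so that a comfort gain is probably the prosthetist's doing. The documents do not support that. Adjustment is conditional on need, and no passage says the socket itself is modified; prosthetic fit is the wording used. Nor is it right that the plan would be blind to adjustment, given the calls and interviews.

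**Conclusion.** The concern holds in a limited form. In a woman whose prosthesis is adjusted for reasons other than fitting Brasthesis, the planned comfort change cannot separate that adjustment from the harness effect. In a woman who is not adjusted, there is nothing to separate on this account.

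The range in the table, 0 to 2 points on a 0-10 scale, rests wholly on the assumed gain per adjusted woman and the assumed number adjusted, and zero is a real possibility. It shows what the data could not rule out; it does not estimate bias. The consequence is for interpretation only. The point merits a change because the endpoint is primary and the remedy is small.

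**What to change.** 1. Reconcile Protocol 6.2 (Brasthesis only at the end) with SAP Aim 2 (both harnesses on the post-interview day). The protocol carries a revision date of July 6, 2023 and the SAP an approval date of 02/10/2022; neither says which schedule governs.
2. On the post-visit day, with both harnesses worn as in the SAP, ask the one-item Socket Comfort Score after each harness on the same prosthesis. Report the paired difference beside the planned pre-to-post change.
3. Record each adjustment with its date as either harness/Brasthesis or prosthesis/socket, and mark in the tables the women whose prosthesis was changed.

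**Cost.** One extra question per woman (five for five completers) and one log line per adjustment. If the protocol's schedule is kept, the traditional harness must also be put on once more; Protocol 6.4 already lets participants return to it at any time. Because of the brief-wear, order and customisation effects in S, the same-day rating supplements the four-week rating and does not replace it. If both harnesses cannot be worn that day, step 3 still identifies the women affected.
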